5.5. Number of Patients and Replacement of Patients Who Discontinue Early

Approximately 25 patients evaluable for response are anticipated to enroll in this study at Vanderbilt University Medical Center.

In general, it is intended that patients will be treated until disease progression or intolerable toxicity. The criteria for patient discontinuation are listed in Sections 9 and 11.

If a patient discontinues study treatment for reasons clearly not related to study treatment, after completing fewer than one planned infusion of avelumab, and/or receiving <75% of the total intended dose of avelumab over the first cycle of treatment + an additional 14 days (i.e. first 28 days after initiating patient's first dose of avelumab), then that patient will be considered not evaluable for response to study treatment and may be replaced with a new patient.

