9.2 Avelumab Infusion

In this clinical trial, the avelumab dose will be 10 mg/kg administered as 1-hour intravenous (IV) infusion every 2 weeks (Q2W). Patient vital signs will be monitored at ≤ 10 minutes prior to avelumab infusion, and ≤ 10 minutes after avelumab infusion. Following avelumab infusions, patients must be observed for 30 minutes post infusion for potential infusion related reactions. See schedule of assessments (Section 7.1) for the specific vital signs that will be monitored.

This dose is the recommended dose administered to more than 480 patients in the ongoing dose-expansion phase of study EMR 100070-001 (see Section 4 for details).

Avelumab will be administered on Day 1 of each cycle after all assessments and procedures have been completed as described in the Schedule of Assessments table (Section 7).

Cycle 2, Day 1 dosing should occur 14 days after Cycle 1, Day 1. In the absence of delayed dosing (e.g. due to an adverse event), every reasonable effort should be made to remain on a consistent schedule of 14-day cycles; but for purpose of accommodating holidays, scheduling limitations, etc, subsequent cycles (i.e. Cycles 3+) may occur up to every 14 days +3 days. Consecutive doses of avelumab must be separated by no fewer than 14 days and, in the absence of adverse event management, no more than 17 days.

Every effort should be made to target infusion timing to be as close to 1 hour as possible. However, given the variability of infusion pumps, time windows of -10 minutes and +20 minutes are permitted (i.e. the scheduled avelumab infusion time is 60 minutes: -10 min/+20 min).

The exact duration of infusion should be recorded in both source documents and data case report forms (CRFs). Possible modifications of the infusion rate for the management of infusion-related reactions are described in Section 11.

The dose amount required to prepare the avelumab infusion solution will be based on the patient's weight in kilograms (kg). All patients should be weighed within 3 days prior to every dose of avelumab.

If a patient experiences either a weight loss or gain $\geq 10\%$ compared to the weight used to calculate the patient's immediately prior dose, then the amount avelumab required for a current dose must be recalculated using the most recent weight obtained.

Avelumab dose reduction for toxicity management is not permitted, however avelumab administration may be held due to adverse event as described in Section 11.

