13.1. Definitions

For purposes of this study, patients should be re-evaluated for response every 8 weeks. Response and progression will be evaluated using the international criteria proposed by the revised Response Evaluation Criteria in Solid Tumors (RECIST) Committee (version 1.1) and immune-related response criteria (irRC). Any evaluable or measurable disease must be documented at screening and reassessed at each subsequent tumor evaluation. If a patient is found to have disease progression by RECIST, at the discretion of the treating physician, the patient may remain on study. Baseline evaluation of disease status by CT or MRI required within 28 days prior to first dose of avelumab. The first scheduled re-scan should be performed and evaluated 7 to 8 weeks after Cycle 1, Day 1 treatment, with subsequent scheduled scans intended every 8 to 9 weeks thereafter. If progression is confirmed by irRC, the patient should typically be removed from study (i.e. in the absence of therapeutic benefit and an alternative agreement and arrangement specified by protocol). If irRC show the patient to not have disease progression, the patient may remain on study.

Evaluable for toxicity: All patients will be evaluable for toxicity from time of their first treatment with avelumab.

Evaluable for objective response: Only those patients who have measurable disease present at baseline, have received at least one cycle of therapy, and have had their disease re-evaluated will be considered evaluable for response. These patients will have their response classified according to the definitions stated below. (Note: Patients who exhibit objective disease progression prior to the end of cycle 1 will also be considered evaluable.)

If a patient discontinues study treatment for reasons clearly not related to study treatment, after completing fewer than one planned infusion of avelumab, and/or receiving <75% of the total intended dose of avelumab over the first cycle of treatment + an additional 14 days (i.e. first 28 days after initiating patient's first dose of avelumab), then that patient will be considered not evaluable for response to study treatment and may be replaced with a new patient.

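### Under 13.1, a patient who stops for an unrelated reason after one of two intended infusions can be both evaluable and replaceable, and nothing bars replacement once the scan is known

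*Combined protocol and SAP*

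**What the plan says.** Section 13.1 defines who counts for response in two consecutive paragraphs.

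The first requires measurable disease at baseline and says that patients who "have received at least one cycle of therapy, and have had their disease re-evaluated will be considered evaluable for response". A note adds: "Patients who exhibit objective disease progression prior to the end of cycle 1 will also be considered evaluable".

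The second works by exclusion. It opens "If a patient discontinues study treatment for reasons clearly not related to study treatment, after completing fewer than one planned infusion of avelumab", adds as an alternative or further condition "receiving <75% of the total intended dose of avelumab over the first cycle of treatment + an additional 14 days", and concludes "then that patient will be considered not evaluable for response to study treatment and may be replaced with a new patient". Section 5.5 repeats this exclusion.

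Three other sections bear on the point:

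- Section 8.3 asks for a disease assessment when treatment stops for a reason other than progression. It is due within 28 days of the last avelumab dose and before other anti-cancer therapy.
- Section 17.4 puts eligible patients who had two weeks of study drug in the main analysis, which it names as that of clinical benefit rate. It treats response categories 4 to 9 as failures and says that errors of schedule or administration are not grounds for exclusion from the response analysis.
- Sections 17.1 and 17.3 base the go decision on four or more responses among 25 treated. Sections 5.5 and 17.2 plan for about 25 evaluable.

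**The concern.** The two paragraphs of 13.1 can give opposite answers for one patient, and the plan does not say which governs. Replacement is a permission, not a requirement. Neither 5.5 nor 13.1 says it must be decided before a post-baseline scan has been read. Membership of the 25 could therefore be settled with the outcome in view.

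The primary decision turns on four responses in 25, so a few discretionary replacements matter. If they fell mainly on non-responders, both the reported ORR and the chance of a false go would rise, even with every response scored correctly.

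**Working it through.** **1. Dose fraction.** Cycles last 14 days with one infusion on Day 1 of each (2.3, 9.2), and "Cycle 2, Day 1 dosing should occur 14 days after Cycle 1, Day 1". The window is 28 days (5.5, 13.1).

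- Intended infusions: 28/14 = 2.
- One infusion: 1/2 = 50%, below 75%. The threshold equals 0.75 × 2 = 1.5 infusions.
- Section 9.2 states "Avelumab dose reduction for toxicity management is not permitted", so the fraction normally moves in whole infusions.
- The limb about fewer than one infusion adds nothing, because less than 1/2 is already under 75%.

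This takes the window as Days 1 to 28. If a Day 29 dose were counted, one infusion would be 1/3 = 33%, and even two would be 2/3 = 67% and fail.

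**2. One patient under each rule.** Take an eligible patient with measurable disease who has one infusion, completes cycle 1, stops for a clearly unrelated reason before the second infusion, and has a scan showing no response.

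| Rule | Result |
|---|---|
| 13.1, first paragraph | Evaluable, non-responder |
| 13.1, second paragraph, and 5.5 | Not evaluable, may be replaced |
| 17.4 | In the main analysis; failure if in categories 4 to 9 |
| 17.1 and 17.3 | One of the 25 treated |

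The case can arise because of the scan called for in 8.3. It is not certain to arise, because 7.5 waives the end-of-treatment scan if one was done in the previous 28 days.

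**3. Progression.** The note in 13.1 protects progression only up to the end of cycle 1. For progression later in the 28-day window, the answer depends on whether stopping for progression counts as clearly unrelated to study treatment. The documents do not say.

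**4. The plan's own figures.** Inputs from 17.3: n = 25, null ORR 5%, alternative 21%, go at four or more responses, one-sided 5%.

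P(X ≥ 4) = 1 − Σ C(25,x) pˣ(1−p)²⁵⁻ˣ, summed over x = 0 to 3.

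- p = 0.05: 1 − (0.2774 + 0.3650 + 0.2305 + 0.0930) = 0.0341.
- p = 0.21: 0.8013.

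The stated 80% power is reproduced, and the attained type I error is 3.4%.

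**5. Upper bound on the effect.** Suppose k non-responders, and no responders, are replaced. The 25 retained patients then hold every response among 25 + k treated, so the false-go chance is at most P(X ≥ 4) with X ~ Bin(25 + k, 0.05). The value of k is assumed.

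| k | P(go) at true ORR 5% | Four responders as a share of all treated |
|---|---|---|
| 0 | 3.4% | 4/25 = 16.0% |
| 1 | 3.9% | 4/26 = 15.4% |
| 2 | 4.4% | 4/27 = 14.8% |
| 3 | 4.9% | 4/28 = 14.3% |
| 4 | 5.5% | 4/29 = 13.8% |
| 5 | 6.1% | 4/30 = 13.3% |

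The reported rate would be 16.0% in every row.

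**6. Cross-check.** Let f be the share of treated patients who are non-responders and are replaced (also assumed). The rate among those kept is 5%/(1 − f), and P(X ≥ 4) in 25 is 4.7% at f = 10% and 5.6% at f = 15%. It crosses 5% near f = 11.6%, which lies between 3/28 = 10.7% and 4/29 = 13.8%, in agreement with step 5.

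**The case against.** The strongest reply is that 17.4 already settles the matter. It keeps patients with two weeks of drug, counts categories 4 to 9 as failures and refuses exclusion for schedule errors, while 17.1 and 17.3 speak of 25 treated. If those sections govern, a replaced patient stays in as a non-responder and this source of selection disappears. That limits the consequence. It does not remove the conflict, because 5.5 and 13.1 still declare the patient not evaluable, 17.4 names its main analysis for a different rate, and no section says which prevails.

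A second reply concerns reach, and it narrows the point. A reader might infer that anyone given one infusion in the first 28 days is caught. The text does not support that: the 75% rule needs discontinuation for a reason clearly unrelated to treatment. Patients whose second dose is delayed but who stay on treatment, and those who stop for drug toxicity, fall outside it.

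A reader might also infer that early progressors are routinely dropped. Progression before the end of cycle 1 is expressly evaluable. Later progression is exposed only on a reading that the documents do not state. The first scheduled re-scan is at 7 to 8 weeks, and 9.7 allows treatment past initial progression, so such cases would be few.

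Finally, a reader might picture a patient replaced months later after several scans. Resuming at about Day 29 after a missed second dose is possible under 9.2 and 11.1, and the rule sets no deadline for discontinuation. But the heading of 5.5 refers to early discontinuation, so this is a strained use of the rule.

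**Conclusion.** The point stands in a limited form. For a patient who stops for a clearly unrelated reason after one of two intended infusions and has been re-evaluated, 13.1 gives two incompatible answers. Replacement is optional and may follow the scan, and 17.4 adds a third rule. The passages must be reconciled.

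A reader might conclude that the rule inflates the response rate or breaks the 5% error limit. The documents do not support that. The rule takes no account of response, so a scanned responder who stopped could equally be replaced. The figures in the working are upper bounds: they assume that only non-responders are replaced and that replaced patients leave the denominator. Even then, three such replacements stay within 5% (4.9%) and four exceed it (5.5%). The documents give no expected number.

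The change is still worth making, because the plan as written permits outcome-aware replacement in a trial decided on four responses.

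**What to change.** In 5.5 and 13.1, allow replacement only in two situations:

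- no avelumab was received; or
- treatment stopped within 28 days of the first dose, before any post-baseline tumor assessment, for a documented reason other than progression, clinical deterioration, toxicity or death.

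Delete the 75% limb. State, consistently with 17.4, that every other treated patient stays in the ORR denominator as a non-responder unless a response is confirmed. Align the first paragraph of 13.1 and its note with that sentence, so that no competing definition remains. The open question about progression after cycle 1 then no longer affects the denominator.

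The cost is protocol wording in 5.5 and 13.1, checked against 17.4, with no new data. The reported ORR may be slightly lower, and fewer patients would be replaced.

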13.2. Disease Parameters

13.2.1 Measurable

Tumor lesions: Must be accurately measured in at least one dimension (longest diameter in the plane of measurement is to be recorded) with a minimum size of:

- 10mm by CT scan (CT scan slice thickness no greater than 5 mm).
- 10mm caliper measurement by clinical exam (lesions which cannot be accurately measured with calipers should be recorded as non-measurable).
- 20mm by chest X-ray.

Malignant lymph nodes: To be considered pathologically enlarged and measurable, a lymph node must be ≥ 15 mm in short axis when assessed by CT scan (CT scan slice thickness recommended to be no greater than 5 mm). At baseline and in follow-up, only the short axis will be measured and followed.

13.2.2 Non-measurable

All other lesions, including small lesions (longest diameter < 10 mm or pathological lymph nodes with ≥ 10 to < 15 mm short axis) as well as truly non-measurable lesions. Lesions considered truly non-measurable include: leptomeningeal disease, ascites, pleural or pericardial effusion, inflammatory breast disease, lymphangitic involvement of skin or lung, abdominal masses/abdominal organomegaly identified by physical exam that is not measurable by reproducible imaging techniques.

13.2.3 Special considerations regarding lesion measurability

Bone lesions, cystic lesions, and lesions previously treated with local therapy require particular comment:

Bone lesions:

- Bone scan, PET scan or plain films are not considered adequate imaging techniques to measure bone lesions. However, these techniques can be used to confirm the presence or disappearance of bone lesions.
- Lytic bone lesions or mixed lytic-blastic lesions, with identifiable soft tissue components, that can be evaluated by cross-sectional imaging techniques such as CT or MRI can be considered as measurable lesions if the soft tissue component meets the definition of measurability described above.
- Blastic bone lesions are non-measurable.

Cystic lesions:

- Lesions that meet the criteria for radiographically defined simple cysts should not be considered as malignant lesions (neither measurable nor non-measurable) since they are, by definition, simple cysts.
- 'Cystic lesions' thought to represent cystic metastases can be considered as measurable lesions, if they meet the definition of measurability described above. However, if non-cystic lesions are present in the same patient, these are preferred for selection as target lesions.

Lesions with prior local treatment:

- Tumor lesions situated in a previously irradiated area, or in an area subjected to other loco-regional therapy, are usually not considered measurable unless there has been demonstrated progression in the lesion.

13.2.4 Specifications by methods of measurements

Measurement of lesions:

All measurements should be recorded in metric notation, using calipers if clinically assessed. All baseline evaluations should be performed as close as possible to the treatment start and never more than 4 weeks (28 days) before the beginning of study treatment.

Method of assessment:

The same method of assessment and the same technique should be used to characterize each identified and reported lesion at baseline and during follow-up. Imaging-based evaluation should always be done rather than clinical examination unless the lesion(s) being followed cannot be imaged but are assessable by clinical exam.

- Clinical lesions: Clinical lesions will only be considered measurable when they are superficial and ≥ 10 mm diameter as assessed using calipers (e.g. skin nodules). For the case of skin lesions, documentation by colour photography including a ruler to estimate the size of the lesion is suggested. When lesions can be evaluated by both clinical exam and imaging, imaging evaluation should be undertaken since it is more objective and may also be reviewed at the end of the study.
- Chest X-ray: Chest CT is preferred over chest X-ray, particularly when progression is an important endpoint, since CT is more sensitive than X-ray, particularly in identifying new lesions. However, lesions on chest X-ray may be considered measurable if they are clearly defined and surrounded by aerated lung.
- CT, MRI: CT is the best currently available and reproducible method to measure lesions selected for response assessment. Guidelines have defined measurability of lesions on CT scan based on the assumption that CT slice thickness is 5mm or less. When CT scans have slice thickness greater than 5 mm, the minimum size for a measurable lesion should be twice the slice thickness. MRI is also acceptable in certain situations (e.g. for bodyscans).

Ultrasound: Ultrasound is not useful in assessment of lesion size and should not be used as a method of measurement. Ultrasound examinations cannot be reproduced in their entirety for independent review at a later date and, because they are operator dependent, it cannot be guaranteed that the same technique and measurements will be taken from one assessment to the next. If new lesions are identified by ultrasound in the course of the study, confirmation by CT or MRI is advised. If there is concern about radiation exposure at CT, MRI may be used instead of CT in selected instances.

- Endoscopy, laparoscopy: The utilization of these techniques for objective tumor evaluation is not advised. However, they can be useful to confirm complete pathological response when biopsies are obtained or to determine relapse in trials where recurrence following complete response or surgical resection is an endpoint.
- Tumor markers: Tumor markers alone cannot be used to assess objective tumor response. If markers are initially above the upper normal limit, however, they must normalize for a patient to be considered in complete response.
- Cytology, histology: These techniques can be used to differentiate between PR and CR in rare cases if required by protocol (for example, residual lesions in tumor types such as germ cell tumors, where known residual benign tumors can remain). When effusions are known to be a potential adverse effect of treatment (e.g. with certain taxane compounds or angiogenesis inhibitors), the cytological confirmation of the neoplastic origin of any effusion that appears or worsens during treatment can be considered if the

measurable tumor has met criteria for response or stable disease, in order to differentiate between response (or stable disease) and progressive disease.

13.3. Response Criteria

13.3.1 Target lesions

When more than one measurable lesion is present at baseline: All lesions up to a maximum of five lesions total (and a maximum of two lesions per organ) representative of all involved organs should be identified as target lesions, with repeatable measurements recorded and measured at baseline. (In instances where patients have only one or two organ sites involved, a maximum of two and four lesions will respectively be recorded.)

13.3.2 Evaluation of Target Lesions

Complete Response (CR): Disappearance of all target lesions. Any pathological lymph nodes (whether target or non-target) must have reduction in short axis to <10 mm.

- Partial Response (PR): At least a 30% decrease in the sum of diameters of target lesions, taking as reference the baseline sum diameters.
- Progressive Disease (PD): At least a 20% increase in the sum of diameters of target lesions, taking as reference the smallest sum on study (this includes the baseline sum if that is the smallest on study). In addition to the relative increase of 20%, the sum must also demonstrate an absolute increase of at least 5 mm. (Note: the appearance of one or more new lesions is also considered progression.)
- Stable Disease (SD): Neither sufficient shrinkage to qualify for PR nor sufficient increase to qualify for PD, taking as reference the smallest sum of diameters while on study.

13.3.3 Non-target lesions

All other lesions (or sites of disease) including pathological lymph nodes should be identified as non-target lesions and should also be recorded at baseline. Measurements are not required and these lesions should be followed as 'present', 'absent', or in rare cases 'unequivocal progression'. In addition, it is possible to record multiple non-target lesions involving the same organ as a single item on the case record form (e.g. 'multiple enlarged pelvic lymph nodes' or 'multiple liver metastases').

13.3.4 Evaluation of Non-Target Lesions

Complete Response (CR): Disappearance of all non-target lesions and normalization of applicable tumor marker level. All lymph nodes must be non-pathological in size (<10mm short axis).

Non-CR/Non-PD: Persistence of one or more non-target lesion(s) and/or maintenance of applicable tumor marker level above the normal limits.

Progressive Disease (PD): Unequivocal progression of existing non-target lesions. (Note: the appearance of one or more new lesions is also considered progression.)

13.3.5 Evaluation of Best Overall Response

The best overall response is the best response recorded from the start of the study treatment until the end of treatment taking into account any requirement for confirmation. The patient's best overall response assignment will depend on the findings of both target and non-target disease; and will also take into consideration the appearance of new lesions, as well as post-treatment assessments and any new therapy introduced before progression. Furthermore, depending on the nature of the study and the protocol requirements, it may also require confirmatory measurement. Specifically, in non-randomized trials where response is the primary endpoint, confirmation of PR or CR is needed to deem either one the 'best overall response'.

Time point response:

Target Lesions	Non-Target Lesions	New Lesions	Overall Response
CR	CR	No	CR
CR	Non CR/Non PD	No	PR
CR	Not evaluated	No	PR
PR	Non PD or not all evaluated	No	PR
SD	Non PD or not all evaluated	No	SD
Not all evaluated	Non PD	No	NE
PD	Any	Yes or no	PD
Any	PD	Yes or no	PD
Any	Any	Yes	PD

CR= complete response, PR= partial response, PD= progressive disease, SD= stable disease, NE= not evaluable.

* In exceptional circumstances, unequivocal progression in non-target lesions may be accepted as disease progression.

Note: Patients with a global deterioration of health status requiring discontinuation of treatment without objective evidence of disease progression at that time should be reported as "symptomatic deterioration." Every effort should be made to document the objective progression even after discontinuation of treatment.

